The primary endpoint is a temporary suppression of epileptic spikes. With assessments of spike rates at weeks 2, 4, 8, 16, and 24, the study will allow estimation of how temporary a suppression is achieved by the one-week treatment. The routine dEEG sessions typically collect dEEG for over an hour, and spike rates per hour will be the standard metric. To be successful, and to warrant progression to a randomized clinical trial, this clinical feasibility study must demonstrate successful targeting and suppression of the epileptogenic zone, as evidenced by temporary but statistically significant spike suppression in contrast to the pre-treatment baseline. All spike rates (baseline, treatment, and follow-up) will be counted as spikes per hour and classified in relation to waking or sleep stage (N1, N2, N3).

Secondary Endpoints and Study Success

The secondary endpoint is monthly suppression of seizures, assessed by the seizure diary each month for six months following treatment, in comparison to the mean seizure frequency for the one-month pre-treatment evaluation baseline. It is clearly advantageous if there is seizure as well as spike suppression as we plan the design of the pivotal trial.

Additional secondary endpoints will be (1) any improvement of cognitive function testing beyond the practice effect (estimated from norms and the improvement in the sham control group); (2) any improvement in quality of life ratings.

Study Monitoring Committee

The safety and comfort decisions for each patient are made by the epileptologist at each site. The safety, comfort, and efficacy of each treatment protocol across sites are reviewed by the Study Monitoring Committee. Vigilance will be maintained throughout the pivotal study to insure safety (no provoked seizures and no adverse effect to non target brain regions). Treatment will be discontinued for any patient that shows treatment-induced seizures, defined as seizures that are not the patient's typical seizures or that occur twice as frequently as the patient's typical seizures, as assessed during baseline. If there are more than five patients with worsening seizures (meeting escape criteria as stated above), the treatment will be suspended at that site. The Study Monitoring Committee (and the FDA when possible) will decide if the trial with that treatment should be terminated at all sites.

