At each site, careful attention will be given to the dosage that patients tolerate well, primarily in relation to maintaining adequate comfort with the treatment current and the lidocaine anesthetic. We are confident from the pre-clinical studies that these protocols are tolerated by normal volunteers, and should be comfortable patients with epilepsy. If the electrical dosage needs to be adjusted for individual patients, then the quantitation of cortical target dosage and the dose-response analysis will provide an indication of dosage efficacy (at varying dosage levels) across the entire trial.

Quantitating the Estimated Effective Dose

Because the effective (surface normal) targeting varies across patients according to the location of the epileptogenic zone, the data analysis will attempt to predict the criterion of seizure suppression from the quantitation of effective dosage for each patient. Eventually, this quantitative prediction may allow indications for use that are gauged in relation to the estimated targeting effectiveness in the pre-treatment GTEN planning process. If successful, the adaptive estimation of effective cortical dosage would allow the physician to (1) localize the epileptogenic zone with dEEG, (2) conduct an initial analysis GTEN Planning Module of the effective dose that can be delivered with the 256 array with the 2 mA dose level, (3) conduct a pilot session to determine if the patient is comfortable with the dose required for efficacy, and then (4) discuss with the patient whether GTEN treatment is a worthwhile option. Post hoc analysis of the effective targeting in the clinical feasibility trial will provide initial evidence of the importance of cortical surface normal targeting dosage in predicting seizure suppression.

Power Analysis and Missing Data Analysis

This clinical feasibility trial will test for a statistically significant suppression of epileptic spikes at several time points (weeks, 2, 4, 8, 16, and 24) following treatment in contrast to the average of two dEEG evaluations during the one-month baseline. Without previous results on the Pulsed GTEN treatment, it is difficult to estimate effect sizes for power analysis for this one-week treatment intervention.

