As pointed out by the FDA reviewer, an extensive statistical plan may not be warranted for a feasibility study. Furthermore, although we have considered the results of the rTMS study of Sun et al (Sun et al., 2012) to provide some indication of effect size, we agree that we have little basis for estimating the power required for determining the significance of spike suppression with GTEN therapy. We do plan to follow the reviewer's suggestion to compare spike rates following treatment to those from the baseline assessment with a one-sided t-test with a significance level of 0.025.

At the same time, we recognize that we are proposing to evaluate two protocols (Sustained Blocked tDCS and Pulsed GTEN), and must have sufficient numbers of patients to demonstrate feasibility, and to examine the significance of spike suppression, for either treatment protocol. If one protocol is effective and the other is not, we propose to stop enrolling patients for the ineffective protocol and focus recruitment on the effective one to demonstrate efficacy for a pivotal study.

Study Procedures

Informed Consent

Both the recruitment information and the informed consent document explain several aspects of the study:

- GTEN (Geodesic Transcranial Electrical Neuromodulation) is a method of applying small electrical currents through the head in order to achieve a lasting decrease in the neuronal activity of the epileptogenic (seizure-causing) zone of cortex. The experimental treatment protocols have been designed on the basis of previous scientific studies. For the Pulsed TEN, the studies have suggested suppression of epileptic seizures with Transcranial Magnetic Stimulation (in the Fregni, et al., 2006 and Sun, et al., 2012 trials). GTEN is used instead of TMS because of the ability to control the targeting of cortical sites more precisely, as guided by the dEEG fields of the epileptiform discharges. In addition, GTEN is able to target epileptogenic zones in deep as well as superficial cortical sites.

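### The go/no-go rule names no primary week and does not control alpha across five follow-up tests; if one significant week suffices, the false-success rate is about 7-10%, not 2.5%

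*Protocol*

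**What the plan says.** Under Primary Endpoint and Study Success, the protocol states: "The primary endpoint is a temporary suppression of epileptic spikes". No week is attached to it. The same section makes progression to a randomized trial depend on successful targeting and suppression, "as evidenced by temporary but statistically significant spike suppression in contrast to the pre-treatment baseline". It also says that the repeated assessments will allow an estimate of how long suppression lasts.

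Under Power Analysis and Missing Data Analysis, the trial "will test for a statistically significant suppression of epileptic spikes at several time points (weeks, 2, 4, 8, 16, and 24"), with each week taken "in contrast to the average of two dEEG evaluations during the one-month baseline". The sponsor then adopts the FDA's suggestion to "compare spike rates following treatment to those from the baseline assessment with a one-sided t-test with a significance level of 0.025". The level is not divided across weeks. No sample size, standard deviation or effect size is stated, and the section says that "it is difficult to estimate effect sizes for power analysis for this one-week treatment intervention".

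The assessment weeks are not the same throughout:

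- Weeks 2, 4, 8, 16 and 24: Follow up Protocol, Primary Endpoint and Study Success, the power section and Table 2.
- Weeks 2, 8, 16 and 24: the end of Therapeutic Mode of Action.
- Weekly for three weeks, then week 8: Monitoring of Risk.

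**The concern.** The protocol itself fixes the time points, the test, the level and the decision that hangs on the result. It does not say which of the five results decides, or how they combine. Success requires only temporary suppression, so a result that is significant at one week and not at the others is compatible with the criterion. If one such week is enough, the decision is an uncorrected choice among five tests, each at 0.025.

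The trial has no control group. This comparison with baseline is therefore the statistical part of the decision to start a randomized trial. Leaving the deciding contrast open lets it be chosen after the data are seen. A device with no effect would then be carried forward more often than the stated level implies.

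**Working it through.** **Inputs from the protocol.** Five follow-up weeks, a one-sided t-test at 0.025, and a shared comparator (the mean of two baseline recordings). The protocol gives no sample size and no correlation between visits, so both are assumed below and shown as ranges.

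**The plan's own figure.** The only stated figure is the level of 0.025. A single paired one-sided t-test keeps it: simulated under no effect at n = 10, 15 and 20, the week 2 test alone rejected in 2.3-2.5% of runs.

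**Independent tests (upper bound).** 1 - (1 - 0.025)^5 = 1 - 0.975^5 = 0.119. For four weeks, 1 - 0.975^4 = 0.096.

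**Correlation from the shared baseline.** Let each recording have error variance 1, let baseline errors be independent, and let follow-up errors correlate at rho. Each change score has variance 1 + 1/2 = 3/2. Two change scores have covariance rho + 1/2. Their correlation is therefore r = (rho + 1/2)/(3/2).

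**Any-of-five rate for equicorrelated tests.** With c = 1.96, the rate is 1 - ∫ φ(u) Φ((c - √r·u)/√(1 - r))^5 du. It was checked by simulating 40,000 sets of paired t-tests per cell.

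| Assumed rho between follow-ups | r between changes | Large-sample rate | Simulated, n = 10 / 15 / 20 |
|---|---|---|---|
| 0 | 0.33 | 10.3% | 10.4 / 10.4 / 10.6% |
| 0.3 | 0.53 | 8.9% | 9.3 / 9.1 / 9.0% |
| 0.6 | 0.73 | 7.1% | 7.5 / 7.2 / 7.4% |

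**Wider range.** The large-sample rate is 11.9% at r = 0 and 5.1% at r = 0.9.

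**Four weeks instead of five.** With the weeks listed in Therapeutic Mode of Action, the rate is 9.6% if independent and 8.6% at r = 1/3.

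**Candidate remedies under no effect.**

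- One pre-named week gives 2.5%. A fixed-order sequence starting from that week also gives 2.5%, because nothing later is tested unless the first test succeeds.
- One test on the mean of the five changes gave 2.4-2.6% in the same simulation.
- Testing every week at 0.025/5 = 0.005 gives 2.4% at r = 0.2 and 1.6% at r = 0.75.

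**The case against.** The strongest objection is that no sentence says one significant week is enough. The protocol speaks of comparing rates after treatment with baseline "with a one-sided t-test with a significance level of 0.025", in the singular. That could mean one pooled comparison, whose error rate would be 2.5%. The repeated weeks also have a descriptive purpose of their own, which is to show how long suppression lasts. This stands in part: the any-of-five rule is an inference, so the 7-10% is conditional on it. It does not remove the problem, because the same section plainly plans tests at several weeks and nothing in the document chooses between the two readings.

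A second objection is that this is an uncontrolled feasibility study, that the FDA suggested the t-test, and that the protocol records that an extensive statistical plan may not be warranted. This stands as to severity: a false pass leads to a randomized trial, not to an efficacy claim. It does not excuse the omission, since naming one contrast takes a sentence.

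A reader might go further and infer from "spike rates per hour will be the standard metric" that power is lost by testing untransformed rates, and that a log-scale test is needed. The documents do not support that:

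- They give no sample size, spread or distribution. Naming a counting unit does not exclude a transformation, which is commonly left to the SAP.
- The 50% reduction in the Rationale section is introduced in a paragraph about seizures, so it does not show that spike suppression is proportional.
- A log test could do harm here. Baseline Evaluation gives two-hour recordings, while Table 2 gives 30 minutes at follow-up unless sleep EEG is needed. Shorter recordings give noisier counts, which lowers the mean log. I simulated no effect with an assumed mean of 20 spikes per hour, between-patient log-SD 0.8-1.2, session log-SD 0.4-0.6 and 0.5 added to each rate. The log test rejected in about 4-5% of runs at n = 15 and in up to about 10% at n = 30.

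**Conclusion.** The concern holds in this form: the success rule names no primary week, no rule for combining weeks and no control of error across them. On the natural but not explicit reading that any one significant week counts, the false-success rate is about 7-10% for follow-up correlations of 0 to 0.6. That is roughly three to four times the stated 2.5%. Over a wider range of correlations it is 5-12%, and with a four-week schedule it is at most 9.6%. These figures assume equal error variance at every recording, independent baseline errors and a common correlation between follow-ups. If one pooled test is meant, the rate is 2.5%, and the defect is only that the protocol does not say so. No claim about the measurement scale is made. The point should be fixed before the data are analysed, but it does not undermine a feasibility study.

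**What to change.** In Primary Endpoint and Study Success and in Power Analysis and Missing Data Analysis, name one primary contrast at one-sided 0.025. One workable form: success is decided at week 2. Weeks 4, 8, 16 and 24 are then tested in that order at the same level, stopping at the first non-significant week. The last significant week gives the duration claim, which answers the protocol's own question of how long suppression lasts. Starting early fits the remark in Therapeutic Mode of Action that single-session tDCS suppressed epileptiform activity only over days or weeks. The choice of week remains the sponsor's.

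The cost is wording only, with no added patients or visits. The drawback is that an effect first appearing after week 2 could not be claimed. If the sponsor does not accept that, there are two alternatives:

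- One test on the mean of the follow-up weeks. This dilutes a short-lived effect: suppression present at one of five weeks contributes one fifth of its size to the mean.
- Each week at 0.005, for an overall rate of about 1.6-2.4%. This makes each single week harder to pass.

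In the same edit, reconcile the assessment weeks across Therapeutic Mode of Action, Follow up Protocol, the endpoint and power sections, Monitoring of Risk and Table 2, so that the number and order of tests are fixed.

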G150023/S003/A003
Supplement Request for Amending the IDE for EGI's
Clinical Feasibility Trial
of the Geodesic Transcranial Electrical Neuromodulation
(GTEN 100) for Suppressing Epileptic Discharges
March 2016 Electrical Geodesics, Inc.

Overview

In this supplement (S003/ A003), we corrected the text of the original IDE (an obsolete version was used in S003/ A002). We request the following modifications to the IDE:

- Remove references to the “blocked sustained tDCS” protocol.
- Add a “probe treatment evaluation” protocol.
- Propose that GTEN treatment may be applied during sleep if the patient’s spikes were recorded during sleep.
- Propose to extend the inclusion to patients with temporal lobe as well as neocortical foci for their interictal discharges.

Changes Requested	Reason for Change	Located on Page:
Drop reference to Blocked Sustained tDCS Protocol	Only the Pulsed GTEN Protocol will be used	Multiple pages, marked in red.
Specify 2 US and 1 China sites	No funding for other US sites	28
Describe Probe Treatment and Evaluation	Pilot Treatment for Brief Safety and Feasibility Test	30
Propose GTEN treatment during sleep if possible	Many patients show most spikes during sleep during the evaluation sessions	33, 34
Propose including patients with primary temporal lobe foci	Most patients show medial temporal as well as neocortical foci	31, 35
Reformat the Informed Consent Document for the UW IRB Format, plus include the probe test	The UW IRB requires its own Consent Form; plus the probe test was added	37, 37

Overview to Original IDE Request (at the end of Q140561):

[EGI requests an Investigational Device Exemption (IDE) for the GTEN 100, following FDA's guidance that this device presents significant risk when used to suppress spikes and seizures in adults and adolescents with epilepsy. We have now revised our analysis of risk, and the mitigation of that risk, in this proposal for a clinical feasibility trial. The purpose of this trial is to determine safety and preliminary evidence of efficacy of the GTEN 100 for temporary suppression of epileptic discharges (spikes). If the clinical feasibility trial proves successful, we would then propose a pivotal trial, to evaluate suppression of seizures, in a future presubmission request.

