The resulting bEIT protocol is not the ill-posed imaging reconstruction of classical EIT, but a well-posed fitting of the conductivity to each tissue compartment (whose image or geometry is now easily obtained from MRI or an MRI atlas). When applied within the GTEN Planning Module, the bEIT validation (**Figure 6**) can be completed through impressing high frequency (200 Hz) low power (10 μ A) signals between the source and sink electrodes that were selected to optimize cortical targeting in the GTEN Planning Module. If the measured potentials (from the non-targeting electrodes, demodulated at the current delivery frequency) fit the prediction, then the delivered currents, the electrical head model, and the distribution of currents throughout the volume used in the GTEN Planning Module are verified as accurate.

Software Life Cycle and Risk Management

The GTEN 100 software, including the Net Station GTEN Control Interface and the GTEN Planning Module, have been developed under EGI's Quality System for a moderate level of concern. EGI's Quality System is audited internally on a regular basis, and it is audited externally by VDE. Design documents for the GTEN 100 include the Design Concept Report, Marketing Requirements Document, and Software Requirements Specification. Key functional components of the software have been designed and tested at the unit level, with regular regression testing and hazard reviews.

Risks of GTEN Treatment and Mitigation of Risks

The goal of GTEN treatment is to safely decrease the excitability of the cortex in order to suppress seizures. Whereas conventional tDCS (with large sponge electrodes) involves weak currents (and is well within limits for safety), it may not be as effective as rTMS, which induces larger currents in the brain. Furthermore, the higher current levels induced by rTMS are well within safety limits for tissue damage, and there is now fairly extensive evidence that slow rTMS (which we emulate with our protocol) has a very low risk of causing seizures. We therefore increased the GTEN current to 2 mA total, added lidocaine to increase comfort at this level.

We recognize the FDA's determination that, in epileptic patients, the GTEN 100 may present significant risk of worsening seizures or inducing cerebral discharges (possibly leading to kindling). We therefore request an Investigational Device Exemption. In addition, we detail the

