Figure 8 shows an attenuation factor of about 20 X from the current level for multiple scalp electrodes (each at about 4 A/m²) to the cortical surface (peaking at about 0.2 A/m²). A similar calculation from one electrode (the worst case failure situation under less than astronomical odds for creating charge density of 2040 C/m²) shows an attenuation of about 100 X, from about 20 A/m² at the scalp to achieve 0.2A/m² on the cortex. With the attenuation of scalp charge density (2040 C/m²) by head tissues ranging from a factor of 80 to 120, the GTEN 100

normal mode charge density at the brain ranges from 26 C/m² to 17 C/m² or a factor of .0005 (26/52400) to .0003 (17/52400) of the safe limit for current to the brain.

The FDA reviewer cited earlier studies suggesting that the attenuation may be a factor of 30 rather than 100. Our modeling, with accurate skull conductivity from CT and with validation through bEIT studies, provides more accurate justification for the values than these early literature values. Nonetheless, we agree with the FDA that caution is warranted in assuming attenuation. As a result, we propose to mitigate the worst case failure through an additional layer of fault protection circuitry.

Note that (although it was not clearly explained in the previous submission), the GTEN 100 includes circuitry to limit the current per channel to 200 μ A. The fault protection is designed to limit total current assuming this circuit fails.

The GTEN 100 design has now been revised to include a second Sentinel Circuit®, in series with the first one, to insure that failure requires a triple fault (the circuit fault, and failure of both Sentinel Circuits). The Sentinel Circuit is a separate electronic monitor circuit that detects if the current level exceeds the planned 2 mA value (such as if there is a fault in the electronics circuit). In that event, the Sentinel Circuit disconnects the current generator.

Risk of Seizures in Normal Operation

An important risk of the GTEN treatment is the risk of causing seizures. This risk may not be simply related to the level of current, but rather involves the more complex and poorly understood neurophysiology of epilepsy. The evidence on treating epilepsy with both tDCS and rTMS is relevant to assessing the risk of seizures.

Mitigating the Risk of Seizures in Normal Operation

It should be emphasized that patients must agree to maintain their regular anti epileptic medication during the course of the study.

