- There is minimal risk of the treatment. The slow pulsed electrical neuromodulation has been applied in several studies of epilepsy with the TMS procedure, and there is no evidence that it causes seizures. Transcranial electrical stimulation (tDCS) has been applied in several experimental studies of patients with epilepsy, with no evidence that it causes seizures. Nonetheless, there is always a small risk of causing seizures, and medical procedures are in place both to monitor for seizures (with the EEG recording in each session) and to provide first aid if a seizure occurs.

- The primary feeling of the electrical current is a tingling sensation, and there is risk of minor itching and/or scalp pain. A small amount of lidocaine is mixed in the electrolyte to minimize the pain at the electrode site, and the procedures will be adjusted to assure that any discomfort is acceptable to the patient. Each patient should understand that they should speak up if there is any discomfort, that the technician is trained to carefully monitor their comfort level, and that they can quit the treatment at any time by simply saying they want to quit. If there is any emergency, the patient is shown how to simply pull the Geodesic Sensor Net off the head.

Changes to the Harborview Informed Consent Form

The Informed Consent Document (ICD) approved with the GTEN IDE was the EGI Consent Form (GTEN) 12/29/2014. This was rewritten to conform to the format of the University of Washington IRB and approved by the UW IRB. It was then modified to include the probe test (as described in the present protocol) and approved in November 2015. A minor error (stating the probe test was 10 min rather than 17 min) was corrected and the correction was approved March 9, 2016.

The EGI Parental Consent Form approved with the IDE is unchanged, but is not in use because the only active trial site (UW Harborview) is not enrolling adolescents.

Both the EGI IRB Consent form of December 29, 2014 (approved with the IDE) and the UW IRB Consent Form (proposed for this trial with the present Supplement) are attached.

With the exception of the probe test, there are only minor differences in these consent forms, involving the change of format to the UW IRB Consent Form format. Following is a section-by-section summary of the revision, emphasizing where the same information from the (IDE approved) EGI IRB Consent Form is included in the UW IRB Consent Form.

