Purpose of the Study: This was rewritten to be easier to read. It contains a similar description of treating epileptic discharges with small currents applied to the brain.

Study Summary: added to fit the UW format. This section gives an overview of the study. It describes the evaluation and treatment phases, including the probe test, as well as the follow ups sessions. This information is contained in **Study Procedures** in the EGI form.

Study Procedures: This describes the specifics of each baseline, treatment, and evaluation session, including the CVT and QOLIE.

Risk, Stress, or Discomfort: This was rewritten in the required UW format: it describes the same concerns covered in the EGI form: discomfort, skin irritation, adds risk of loss of privacy and psychological risk of ineffective treatment. This mentions the (very minimal) risk of silver allergy (from the AgCl electrodes) that was discussed in an EGI GTEN Hazard Review (since the IDE). It emphasizes risk of seizures and the procedures for seizure monitoring, in a very similar way as the EGI form.

Benefits of the Study: The important statement is that there may be no benefits, similar to the EGI form.

Source of Funding: This was added following the UW format, and explains EGI's financial support for the trial (equipment, 25% salary for [name], and full salary for [name]).

Confidentiality of Research Information: Emphasizes procedures to maintain, and possible limits, similar to the EGI form.

Alternative to Taking Part in This Study and Other Information cover the information that is described in the **Participation** section of the EGI form.

Localizing Epileptiform Discharges (EDs)

The cortical target for GTEN treatment will be determined from ESI applied to epileptiform discharges (spikes) observed during one or more routine (typically half hour or 40 minute) dEEG evaluations. A nap or sleep EEG may also be collected if seizures typically occur during sleep or sleep transition. EDs will typically involve spikes or sharp waves, although more complex seizure-like EDs and clinical seizures recorded during the routine dEEG will be included. A variant of the protocol is identification of the GTEN targeting through localization of seizure onset, such as with long term video dEEG monitoring.

The GTEN Planning Process

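### The risk bullet for recruitment and consent opens with an unqualified minimal-risk statement that does not fit the significant-risk determination recorded in the same protocol

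*Protocol*

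**What the plan says.** Protocol, Study Procedures, Informed Consent: "Both the recruitment information and the informed consent document explain several aspects of the study". One of the listed aspects is risk, and that bullet begins "There is minimal risk of the treatment". Its reasons are that slow pulsed stimulation by TMS and transcranial stimulation by tDCS have each been used in several epilepsy studies without evidence of causing seizures. The bullet then concedes that a small risk of seizures always remains, and it mentions EEG monitoring and first aid.

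Three other places describe the risk differently:

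- Overview to Original IDE Request: the exemption is sought "following FDA's guidance that this device presents significant risk when used to suppress spikes and seizures in adults and adolescents with epilepsy".
- Risks of GTEN Treatment and Mitigation of Risks: the sponsor recognizes the FDA's determination that, in epileptic patients, "the GTEN 100 may present significant risk of worsening seizures or inducing cerebral discharges (possibly leading to kindling"), and requests the exemption for that reason.
- Risk of Seizures in Normal Operation: "An important risk of the GTEN treatment is the risk of causing seizures".

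Changes to the Harborview Informed Consent Form summarizes the rewritten risk section as covering "discomfort, skin irritation, adds risk of loss of privacy and psychological risk of ineffective treatment". It adds silver allergy and says that seizure risk and seizure monitoring are emphasized much as in the sponsor's own form.

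**The concern.** The first sentence of a risk paragraph sets how the rest is read. Here it gives an overall category, minimal, with no qualification, while the sponsor's application proceeds on the footing that the device may present significant risk in this population. Patients with drug-resistant focal epilepsy would be deciding on an uncontrolled, open-label treatment from a summary milder than the one the sponsor accepts. What is at stake is the quality of consent. No endpoint, error rate or sample size depends on it.

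**Working it through.** The main check is a comparison of texts. One small calculation is given at step 6.

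1. **Is the sentence in force?** Yes. It stands in the body of Study Procedures, not in the table of requested changes. The significant-risk wording in the overview is bracketed as carried over from the original request, but nothing withdraws it, and the body section on risks repeats its substance.

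2. **Category.** The bullet says minimal. The overview says the device presents significant risk; the risk section says it may. Both tie this to epilepsy, and the risk section gives it clinical content: worsening seizures and induced discharges that could lead to kindling.

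3. **The sponsor's own description of individual risks.** Seizure induction is called important. Risk of Inducing Kindling of Seizures says people with epilepsy may be at raised risk. Risk of Unwanted Plasticity says understanding of the manipulation is limited and that maladaptive change is possible. The Escape Criteria provide for status epilepticus, a first tonic-clonic seizure and a doubling of seizure frequency.

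4. **The evidence offered for minimal risk.** The bullet cites several TMS and several tDCS studies. The body of the protocol limits what these can carry:
   - Mitigating the Risk of Seizures in Normal Operation cautions that slow rTMS therapy studies in epilepsy are few. The tDCS evidence it cites is two studies of a single session; this trial plans five sessions.
   - Mitigating the Risk of Unwanted Plasticity expects current delivery that is more focal and potentially more effective than in earlier tDCS work, and deeper than in earlier slow rTMS work.
   - Power Analysis and Missing Data Analysis says there are no previous results on the pulsed treatment. The pulsed experience that the protocol describes is testing in normal volunteers.

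   None of these limits appears in the bullet.

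5. **What the bullet does disclose.** It names a small seizure risk, monitoring and first aid. The conflict is therefore confined to the opening category and the unqualified use of the borrowed literature.

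6. **Lidocaine, the one neighbouring risk with a figure.** Mitigating the Risk of Lidocaine Toxicity gives 150 mg of paste per electrode, half of it a 5% cream: 150 × 0.5 × 0.05 = 3.75 mg. For the assumed ten electrodes this is 37.5 mg. The stated threshold is 5 mg/kg × 70 kg, which is 350 mg (the protocol prints 370). The ratio is 37.5/350 = 0.11, or 37.5/370 = 0.10. On the protocol's own assumptions, complete absorption is about one tenth of the threshold, so this risk adds little to the point.

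**The case against.** The strongest defence is that the two statements use different frames. Significant risk is a regulatory finding about a device, worded in the risk section as a possibility, and it is what leads to the exemption request. The bullet is a lay account of expected risk under the planned safeguards. Much of the sponsor's analysis does conclude that residual risk is low: it reads the slow rTMS literature as showing very little seizure risk, thinks serious unwanted plasticity unlikely, and puts lidocaine well below its threshold. It would therefore be too strong to say that the sponsor's whole risk analysis refutes the sentence. The determination nevertheless has stated clinical content, and the low seizure and plasticity estimates are drawn from literature whose limits the protocol itself records. That argues for a qualified sentence, and the present one is unqualified.

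A reader might also infer that the consent forms leave out kindling, unwanted plasticity and lidocaine toxicity, because neither the bullets nor the Harborview summary names them. The documents do not support that. The protocol says both forms are attached, but they are not part of the text available for review. The bullets are offered as several aspects and are not presented as a complete list. The Harborview section summarizes a revision and does not itemize every risk.

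Nor do the documents support the inference that harms would go undetected. EEG is watched during and after treatment and reviewed after sessions, cognition is tested, and diaries and complaints are reviewed with patients and families.

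IRB approval of the Harborview form, and approval of the sponsor's form with the IDE, do not settle whether the protocol's sentence agrees with its own risk sections.

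**Conclusion.** The point holds in a limited form. One sentence that the protocol gives as consent and recruitment content states a risk category that does not agree with the determination the sponsor accepts, with its description of seizure induction as an important risk, or with the limits it places on the supporting literature. The extent is that one sentence. Seizure risk is disclosed directly after it and, by the protocol's account, emphasized in the rewritten form.

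This rests on one assumption: that the informed consent bullets fairly represent what patients are told, as the protocol says. If the forms already qualify the statement, only the protocol text needs correcting. No finding is made about omissions from the forms.

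**What to change.** Delete the minimal-risk sentence or qualify it so that it agrees with the overview and the sections on seizures, kindling and plasticity. The replacement should say that the device was judged to present significant risk when used in people with epilepsy, including possible worsening of seizures or kindling. It should also say that there are no previous results on the pulsed GTEN treatment; testing in normal volunteers can be mentioned as such. The existing sentences on small seizure risk, monitoring and first aid can stay.

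When making the change, the sponsor should compare both attached consent forms with Risk of Inducing Kindling of Seizures and Risk of Unwanted Plasticity, and amend them only where they fall short.

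The cost is consent and recruitment wording, one IRB approval and possibly slightly slower recruitment. The protocol records that a small correction to the Harborview form, the length of the probe test, was approved in March 2016, so the route exists. No treatment procedure, endpoint or analysis changes.
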